### 5.2.3.2 Pembrolizumab Withholding

AEs (both non-serious and serious) associated with pembrolizumab exposure may represent an immunologic etiology. These AEs may occur shortly after the first dose or several months after the last dose of treatment. Pembrolizumab must be withheld for drug-related toxicities and severe or life-threatening AEs as per [Table 8](#). Pembrolizumab dose reductions are not permitted during the trial.

In addition, subjects should receive appropriate supportive care measures as deemed necessary by the treating investigator. Suggested supportive care measures, as described in Section 5.6.2, are also included in ([Table 8](#)).

Dosing interruptions are permitted after Cycle 1 in the case of medical/surgical events or logistical reasons not related to trial therapy (e.g., elective surgery, unrelated medical events, subject vacation, and/or holidays). Subjects should be placed back on trial therapy within 3 weeks of the scheduled interruption, unless otherwise discussed with the Sponsor. The reason for interruption should be documented in the subject's trial record.

**Table 8 Dose Modification and Supportive Care Guidelines for Pembrolizumab for Drug-Related Adverse Events**

Toxicity	Dose Modification Guidelines			Supportive Care Guidelines	
	Hold Treatment for Grade	Timing for Restarting Treatment	Treatment Discontinuation	CTCAE v4.0 Grade	Action / Supportive Care Guidelines
Diarrhea/Colitis	
General Considerations across all Grades: Subjects should be carefully monitored for signs and symptoms of enterocolitis (ie, diarrhea, abdominal pain, blood or mucus in stool, with or without fever) and of bowel perforation (ie, peritoneal signs and ileus).
 
All subjects who experience diarrhea/colitis should be advised to drink liberal quantities of clear fluids. If sufficient oral fluid intake is not feasible, fluid and electrolytes should be substituted via IV infusion.
				
	2-3	Toxicity resolves to Grade 0-1	Toxicity does not resolve within 12 weeks of last dose or inability to reduce corticosteroid to 10 mg or less of prednisone or equivalent per day within 12 weeks	2	
 
Monitor for enterocolitis and bowel perforation. Consider GI consultation and endoscopy.
 
Administer oral corticosteroids.
 
When symptoms improve to Grade 1 or less, steroid taper should be started and continued over no less than 4 weeks.
 

	4	Permanently discontinue	Permanently discontinue	3-4	
 
Monitor for enterocolitis and bowel perforation. Consider GI consultation and endoscopy.
 
Treat with IV steroids followed by high-dose oral steroids.
 
When symptoms improve to Grade 1 or less, steroid taper should be started and continued over no less than 4 weeks.
 

AST, ALT or Increased Bilirubin	2	Toxicity resolves to Grade 0-1	Toxicity does not resolve within 12 weeks of last dose	2	
 
Monitor liver function tests more frequently until returned to baseline values (consider weekly).
 
Treat with IV or oral corticosteroids.
 

	≥3	Permanently discontinue (see exception below) a	Permanently discontinue	3-4	
 
Treat with IV corticosteroids for 24 to 48 hours.
 
When symptoms improve to Grade 1 or less, a steroid taper should be started and continued over no less than 4 weeks.
 

Toxicity	Dose Modification Guidelines			Supportive Care Guidelines	
	Hold Treatment for Grade	Timing for Restarting Treatment	Treatment Discontinuation	CTCAE v4.0 Grade	Action / Supportive Care Guidelines
Type 1 diabetes mellitus (if new onset) including diabetic ketoacidosis (DKA) or Hyperglycemia (≥Grade 3) if associated with ketosis (ketonuria) or metabolic acidosis (DKA)	T1DM or 3-4 hyperglycemia	Hold pembrolizumab for new onset Type 1 diabetes mellitus or Grade 3-4 hyperglycemia associated with evidence of beta cell failure	Resume pembrolizumab when subjects are clinically and metabolically stable	T1DM or 3-4 hyperglycemia	
 
Insulin replacement therapy is recommended for T1DM and for Grade 3-4 hyperglycemia associated with metabolic acidosis or ketonuria.
 
Evaluate subjects with serum glucose and a metabolic panel, urine ketones, glycosylated hemoglobin, and C-peptide.
 

Hypophysitis	2-4	Toxicity resolves to Grade 0-1. Therapy with pembrolizumab can be continued while endocrine replacement therapy is instituted	Toxicity does not resolve within 12 weeks of last dose or inability to reduce corticosteroid to 10 mg or less of prednisone or equivalent per day within 12 weeks	2	
 
Treat with corticosteroids.
 
When symptoms improve to Grade 1 or less, steroid taper should be started and continued over no less than 4 weeks. Replacement of appropriate hormones may be required as the steroid dose is tapered.
 

				3-4	
 
Treat with an initial dose of IV corticosteroids followed by oral corticosteroids.
 
When symptoms improve to Grade 1 or less, steroid taper should be started and continued over no less than 4 weeks. Replacement of appropriate hormones may be required as the steroid dose is tapered.
 

Hyperthyroidism	General Considerations across all Grades: Thyroid disorders can occur at any time during treatment. Monitor subjects for changes in thyroid function (at start of treatment, periodically during treatment and as indicated based on clinical evaluation) and for clinical signs and symptoms of thyroid disorders.				
				2	
 
In hyperthyroidism, non-selective beta-blockers (e.g. propranolol) are suggested as initial therapy.
 

	3	Toxicity resolves to Grade 0-1	Toxicity does not resolve within 12 weeks of last dose or inability to reduce corticosteroid to 10 mg or less of prednisone or equivalent per day within 12 weeks	3-4	
 
Treat with an initial dose of IV corticosteroid followed by oral corticosteroids.
 
When symptoms improve to Grade 1 or less, steroid taper should be started and continued over no less than 4 weeks. Replacement of appropriate hormones may be required as the steroid dose is tapered.
 

	4	Permanently discontinue	Permanently discontinue		
Hypothyroidism		Therapy with pembrolizumab can be continued while thyroid replacement therapy is instituted	Therapy with pembrolizumab can be continued while thyroid replacement therapy is instituted	2-4	
 
Treat with thyroid hormone replacement therapy (levothyroxine or liothyronine), as indicated per standard of care.
 

Toxicity	Dose Modification Guidelines			Supportive Care Guidelines	
	Hold Treatment for Grade	Timing for Restarting Treatment	Treatment Discontinuation	CTCAE v4.0 Grade	Action / Supportive Care Guidelines
Infusion Reaction	General Considerations across all Grades: Signs and symptoms usually develop during or shortly after drug infusion and generally resolve completely within 24 hours of completion of infusion.				
				1 d :	
 
• Increase monitoring of vital signs as medically indicated until the subject is deemed medically stable in the opinion of the investigator.
 
• No premedication at subsequent dosing.
 

	2 b	Toxicity resolves to Grade 0-1		2 c	
 
• Stop Infusion and monitor symptoms.
 
• Additional appropriate medical therapy may include, but is not limited to:                             
 
• IV fluids
 
• Antihistamines
 
• NSAIDS
 
• Acetaminophen
 
• Narcotics
 
 
 
• Increase monitoring of vital signs as medically indicated until the subject is deemed medically stable in the opinion of the investigator.
 
• If symptoms resolve within 1 hour of stopping drug infusion, the infusion may be restarted at 50% of the original infusion rate (e.g., from 100 mL/hr to 50 mL/hr). Otherwise dosing will be held until symptoms resolve and the subject should be premedicated for the next scheduled dose.
 
• Subject may be premedicated 1.5h (± 30 minutes) prior to infusion of pembrolizumab with:                             
 
• Diphenhydramine 50 mg PO (or equivalent dose of antihistamine).
 
• Acetaminophen 500-1000 mg PO (or equivalent dose of antipyretic).
 
 
 

3-4	Permanently discontinue	Permanently discontinue	3 f or 4 g	
 
• Stop Infusion.
 
• Additional appropriate medical therapy may include but is not limited to:                             
 
• IV fluids
 
• Antihistamines
 
• NSAIDS
 
• Acetaminophen
 
• Narcotics
 
• Oxygen
 
• Pressors
 
• Corticosteroids
 
• Epinephrine
 
 
 
• Increase monitoring of vital signs as medically indicated until the subject is deemed medically stable in the
 
	

Toxicity	Dose Modification Guidelines			Supportive Care Guidelines	
	Hold Treatment for Grade	Timing for Restarting Treatment	Treatment Discontinuation	CTCAE v4.0 Grade	Action / Supportive Care Guidelines
					opinion of the investigator. • Hospitalization may be indicated. • Subject is permanently discontinued from further trial treatment administration.
Pneumonitis	2	Toxicity resolves to Grade 0-1	Toxicity does not resolve within 12 weeks of last dose or inability to reduce corticosteroid to 10 mg or less of prednisone or equivalent per day within 12 weeks	2	• Treat with systemic corticosteroids. When symptoms improve to Grade 1 or less, steroid taper should be started and continued over no less than 4 weeks.
	3-4 or Recurrent 2	Permanently discontinue	Permanently discontinue	3-4 or Recurrent 2	• Immediately treat with IV steroids. Administer additional anti-inflammatory measures, as needed. • Add prophylactic antibiotics for opportunistic infections in the case of prolonged steroid administration.
Renal Failure or Nephritis	2	Toxicity resolves to Grade 0-1	Toxicity does not resolve within 12 weeks of last dose or inability to reduce corticosteroid to 10 mg or less of prednisone or equivalent per day within 12 weeks	2	• Treatment with corticosteroids. • When symptoms improve to Grade 1 or less, steroid taper should be started and continued over no less than 4 weeks.
	3-4	Permanently discontinue	Permanently discontinue	3-4	• Treat with systemic corticosteroids. • When symptoms improve to Grade 1 or less, steroid taper should be started and continued over no less than 4 weeks.
All Other Drug-Related Toxicity c	3 or Severe	Toxicity resolves to Grade 0-1	Toxicity does not resolve within 12 weeks of last dose or inability to reduce corticosteroid to 10 mg or less of prednisone or equivalent per day within 12 weeks		
	4	Permanently discontinue	Permanently discontinue		
Note: Permanently discontinue for any severe or Grade 3 (Grade 2 for pneumonitis) drug-related AE that recurs, or any life-threatening event. a For subjects with liver metastasis who begin treatment with Grade 2 AST or ALT, if AST or ALT increases by greater than or equal to 50% relative to baseline and lasts for at least 1 week then subject should be discontinued. b If symptoms resolve within 1 hour of stopping drug infusion, the infusion may be restarted at 50% of the original infusion rate (e.g., from 100 mL/hr to 50 mL/hr). Otherwise dosing will be held until symptoms resolve and the subject should be premedicated for the next scheduled dose. c Subjects with intolerable or persistent Grade 2 drug-related AE may hold study medication at physician discretion. Permanently discontinue study drug for persistent Grade 2 adverse reactions for which treatment with study drug has been held, that do not recover to Grade 0-1 within 12 weeks of the last dose.				d Mild reaction; infusion interruption not indicated; intervention not indicated e Requires infusion interruption but responds promptly to symptomatic treatment (e.g., antihistamines, NSAIDs, narcotics, IV fluids); prophylactic medications indicated for <=24 hrs. f Prolonged (ie, not rapidly responsive to symptomatic medication and/or brief interruption of infusion); recurrence of symptoms following initial improvement; hospitalization indicated for other clinical sequelae (e.g., renal impairment, pulmonary infiltrates) g Life-threatening; pressor or ventilatory support indicated	

### 5.2.4 Timing of Dose Administration

All trial treatments will be administered on an outpatient basis.

Trial treatment should be administered after all procedures/assessments have been completed as detailed on the Trial Flow Chart (Section 6.0).

Table 9 Treatment Schedule for Preladenant Monotherapy in each Arm for each Treatment Cycle

Treatment Arm 1 (Part 1)	Day 1		Days 2 – 21	
	am	pm	am	pm
Preladenant	X*	X	X	X
* The AM dose of preladenant on Day 1 of each cycle is witnessed at the site.				

Table 10 Treatment Schedule for Preladenant and Pembrolizumab in each Arm for each Treatment Cycle

Treatment Arm 2 (Part 1 and Part 2)	Day 1		Days 2 – 21	
	am	pm	am	pm
Preladenant	X*	X	X	X
Pembrolizumab	X			
* The AM dose of preladenant on Day 1 of each cycle is witnessed at the site.				

During the study (in Part 1 and Part 2, and in Arm 1 and Arm 2), starting on Day 1 of Cycle 1, preladenant will be administered orally BID (twice a day) approximately every 12 hours on each day of a 21-day treatment cycle. Preladenant may be administered up to 4 hours before or after the scheduled time for preladenant oral intake. All capsules comprising a dose should be taken within approximately 15 minutes (See Pharmacy Manual).

In Arm 2 (Part 1 and Part 2), on Day 1 of each 21-day cycle, after preladenant administration in the morning, pembrolizumab will be administered at a fixed dose of 200 mg as a 30-minute IV infusion.

Sites should make every effort to target the pembrolizumab infusion timing to be as close to 30 minutes as possible. However, given the variability of infusion pumps from site to site, a window of -5 minutes and +10 minutes is permitted (i.e., infusion time is 30 minutes: -5 min/+10 min) (See Pharmacy Manual).

Trial treatment of pembrolizumab may be administered up to three days before or after the scheduled Day 1 of each cycle due to administrative reasons (up to three days after treatment allocation is permitted).

The Pharmacy Manual contains specific instructions for the handling of preladenant and for the preparation of the pembrolizumab infusion fluid and administration of infusion solution.

### 5.2.5 Trial Blinding

This is an open-label trial; therefore, the Sponsor, investigator and subject will know the treatment administered.

### **5.3 Randomization or Treatment Allocation**

Treatment allocation will occur centrally using an interactive voice response system / integrated web response system (IVRS/IWRS). There are 2 treatment arms. Subjects will be allocated to 1 of 2 treatment arms: preladenant monotherapy (Arm 1) or preladenant in combination with pembrolizumab (Arm 2) using an IVRS/IWRS in Part 1.

In Part 1 of the study, treatment will be allocated by non-random assignment. Enrollment into the preladenant + pembrolizumab combination treatment arm (Arm 2) will begin once all subjects complete 1 cycle of preladenant monotherapy in Arm 1 and complete the DLT evaluation, and a dose finding decision has been made. This ensures that the starting dose of preladenant in the combination arm will be at least 1 level below the dose being tested in the preladenant monotherapy arm. When both treatment arms are open for enrollment, IVRS/IWRS will alternate subject assignment between Arm 1 and Arm 2 starting with Arm 1. For example, once the 50 mg BID dose cohort of Arm 1 (preladenant monotherapy) and the 25 mg BID dose cohort of Arm 2 (preladenant + pembrolizumab) are open for enrollment, the first subject will be allocated to Arm 1, the second subject will be allocated to Arm 2, the third subject will be allocated to Arm 1, etc. Each new dose cohort will open for enrollment without delay once the 21-day DLT observation period of the previous dose cohort is completed and a dose escalation decision is made. When Part 2 is open for enrollment, IVRS/IWRS will assign subjects to one of two cohorts by tumor type.

Subjects participating in this trial will be allocated by non-random assignment.

### **5.4 Stratification**

No stratification based on age, sex or other characteristics will be used in this trial.

### **5.5 Concomitant Medications/Vaccinations (Allowed & Prohibited)**

Medications or vaccinations specifically prohibited in the exclusion criteria are not allowed during the ongoing trial. If there is a clinical indication for any medication or vaccination specifically prohibited during the trial, discontinuation from trial therapy or vaccination may be required. The investigator should discuss any questions regarding this with the Sponsor Clinical Director. The final decision on any supportive therapy or vaccination rests with the investigator and/or the subject's primary physician. However, the decision to continue the subject on trial therapy or vaccination schedule requires the mutual agreement of the investigator, the Sponsor and the subject.

#### **5.5.1 Acceptable Concomitant Medications**

All treatments that the investigator considers necessary for a subject's welfare may be administered at the discretion of the investigator in keeping with the community standards of medical care. All concomitant medication will be recorded on the case report form (CRF) including all prescription, over-the-counter (OTC), herbal supplements, and IV medications and fluids. If changes occur during the trial period, documentation of drug dosage, frequency, route, and date may also be included on the CRF.

All concomitant medications taken by the subject from the date of first dose of trial treatment through 30 days after the last dose of trial treatment should be recorded. Concomitant medications administered after 30 days after the last dose of trial treatment should be recorded for SAEs and ECI as defined in Section 7.2.

Bisphosphonate or denosumab therapy is allowed as long as it is begun at least 2 weeks prior to treatment allocation.

### **5.5.2 Prohibited Concomitant Medications**

Subjects are prohibited from receiving the following therapies during the Screening and Treatment Phase (including retreatment for post-complete response relapse) of this trial:

- Antineoplastic systemic chemotherapy or biological therapy
- Immunotherapy not specified in this protocol (with the exception of denosumab as noted above in Section 5.5.1)
- Chemotherapy not specified in this protocol
- Investigational agents other than preladenant and pembrolizumab
- Radiation therapy
  - Note: Radiation therapy to a symptomatic solitary lesion or to the brain may be allowed at the Investigator's discretion.
- Live vaccines within 30 days prior to the first dose of trial treatment and while participating in the trial. Examples of live vaccines include, but are not limited to, the following: measles, mumps, rubella, chickenpox, yellow fever, rabies, BCG, and typhoid vaccine. Seasonal influenza vaccines for injection are generally killed virus vaccines and are allowed; however, intranasal influenza vaccines (e.g. FluMist®) are live attenuated vaccines and are not allowed.
- Systemic glucocorticoids for any purpose other than to modulate symptoms from an event of clinical interest of suspected immunologic etiology (see Section 5.5.2.2). The use of physiologic doses of corticosteroids may be approved after consultation with the Sponsor.
  - Note: Inhaled steroids are allowed for management of asthma.

Subjects who, in the assessment by the investigator, require the use of any of the aforementioned treatments for clinical management, should be removed from the trial. Subjects may receive other medications that the Investigator deems to be medically necessary. Section 5.1.3 - Subject Exclusion Criteria describes other medications that are prohibited in this trial.

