### 5.2.1.4 Tolerability Evaluation Rules and Dose Escalation

Four dose levels of preladenant are planned in Part 1 ([Table 5](#) and [Table 6](#))

The starting dose (DL1) of preladenant is 25 mg BID. Dose escalation will continue as outlined above (Section 5.2.1.2) according to mTPI dose finding rules.

Table 5 Dose Levels for Preladenant Monotherapy (Part 1: Arm 1)

Arm 1	Preladenant (BID)	
	mg per dose	mg per day
DL-1	10	20
DL1	25	50
DL2	50	100
DL3	100	200
DL4	200	400

Table 6 Dose Levels for Preladenant and Pembrolizumab (Part 1: Arm 2)

Arm 2	Preladenant (BID)		Pembrolizumab (Q3W)
Dose Levels	mg per dose	mg per day	IV Infusion (mg per dose)
DL-1	10	20	200
DL1	25	50	200
DL2	50	100	200
DL3	100	200	200
DL4	200	400	200

Each individual subject will be assigned to a single dose level of study therapy. Intra-subject dose escalation is not allowed. Individual patient dose interruptions and/or dose decreases for preladenant may be implemented based on toxicity as described in Section 5.2.3.1. However, dose adjustments should not be made during the DLT observation period without discussion with the Sponsor. In Arm 2, pembrolizumab administration can be delayed or interrupted but will not be de-escalated see Section 5.2.3.2.

The decision to enroll subjects in the next dose level will be made by the sponsor in consultation with the participating investigators after reviewing the safety and any available PK data of the previous dose level(s).

Subjects may continue on treatment until disease progression, unacceptable toxicity, investigator's decision to withdraw the subject, withdrawal of consent, development of an inter-current condition precluding further administration of study treatment, pregnancy of the subject, failure to comply with dosing evaluations or other study requirements, or administrative reasons requiring cessation of treatment, at which point they will be discontinued from the study.

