#### **5.5.2.1 Prohibited Concomitant Medications for Preladenant**

Specific restrictions for preladenant administration (Arm 1 and Arm 2) during the course of the trial are listed. These are based on the current known metabolism of the drugs as described. Restrictions may be removed if indicated by emergent data from drug-drug interaction trials. Any medications/therapies no longer contraindicated will be communicated

to the site by an administrative letter. The following medications/therapies are not permitted from 2 weeks prior to Day 1 through 2 weeks after the study treatment period.

For subjects who, in the assessment of the investigator, require the use of any of the aforementioned treatments for clinical management should be discontinued. Subjects may receive other medications that the investigator deems to be medically necessary.

- Inhibitors/inducers/substrates of CYP3A4 and substrates for CYP2C8 enzymes.

Preladenant is a competitive and irreversible metabolism-dependent inhibitor of cytochrome P450 (CYP) 3A4, a substrate of CYP3A4, and a direct competitive inhibitor of CYP2C8. As such, concomitant use of other drugs that are identified in [Table 11](#) as strong inducers, strong or moderate inhibitors, or substrates (characterized with a narrow therapeutic range) of CYP3A4 or CYP2C8, is prohibited while the subject is enrolled in this study.

If the use of a CYP3A4 or CYP2C8 medication listed in [Table 11](#) is medically necessary, and an alternate therapeutic agent is not available, then the subject must discontinue treatment with preladenant.

Preladenant may potentially inhibit the activity of other CYP3A4 or CYP2C8 substrates that are not identified as prohibited in [Table 11](#). Caution and close drug monitoring is strongly advised when preladenant is administered concomitantly with other CYP3A4 or CYP2C8 substrates. See [Table 11](#) for more detailed information regarding adverse effects of CYP3A4 substrates with a narrow therapeutic range.

Investigators should check an actively updated list of drugs that are clinically relevant substrates, inducers or inhibitors of cytochrome P450, including CYP3A4 (<http://medicine.iupui.edu/clinpharm/ddis/table.asp>) as well as the product labeling of these compounds for reference.

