## **5.8 Subject Withdrawal/Discontinuation Criteria**

### **5.8.1 Discontinuation of Treatment**

Discontinuation of treatment does not represent withdrawal from the trial.

As certain data on clinical events beyond treatment discontinuation may be important to the study, they must be collected through the subject's last scheduled follow-up, even if the subject has discontinued treatment. Therefore, all subjects who discontinue trial treatment prior to completion of the treatment period will still continue to participate in the trial as specified in Section 6.0 - Trial Flow Chart and Section 7.1.5. – Visit Requirements .

Subjects may discontinue treatment at any time for any reason or be dropped from treatment at the discretion of the investigator should any untoward effect occur. In addition, a subject may be discontinued from treatment by the investigator or the Sponsor if treatment is inappropriate, the trial plan is violated, or for administrative and/or other safety reasons. Specific details regarding procedures to be performed at treatment discontinuation are provided in Section 7.1.4 – Other Procedures.

A subject must be discontinued from treatment but continue to be monitored in the trial for any of the following reasons:

- The subject or subject's legally acceptable representative requests to discontinue treatment.
- Non-compliance with trial treatment or procedure requirements.
- A confirmed positive serum pregnancy test.
- Confirmed radiographic disease progression outlined in Section 7.1.5 (exception if the Sponsor approves treatment continuation).
  - A subject with confirmed radiologic progression may continue to receive study treatment, after consultation with the Sponsor, if the investigator deems the subject is receiving clinical benefit or value from treatment.
- Unacceptable adverse experiences as described in Section 7.2.
- Intercurrent illness other than another malignancy as noted above that prevents further administration of treatment.
- Investigator's decision to discontinue treatment.
- Recurrent Grade 2 pneumonitis.
- Progression or recurrence of any malignancy, or any occurrence of another malignancy that requires active treatment.
- Completion of 35 treatments with preladenant and/or pembrolizumab.

Note: 35 cycles (approximately 2 years) are calculated from the first dose

- Administrative reasons.

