### **5.8.2 Withdrawal from the Trial**

A subject must be withdrawn from the trial if the subject or subject's legally acceptable representative withdraws consent from the trial.

If a subject withdraws from the trial, they will no longer receive treatment or be followed at scheduled protocol visits.

Specific details regarding procedures to be performed at the time of withdrawal from the trial including the procedures to be performed should a subject repeatedly fail to return for scheduled visits and/or if the study site is unable to contact the subject, as well as specific details regarding withdrawal from Future Biomedical Research are outlined in Section 7.1.4 – Other Procedures.

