#### **7.1.1.6.2 Concomitant Medications**

The investigator or qualified designee will record medication, if any, taken by the subject during the trial through the Post-Treatment Safety Follow-Up visit, 30 days after the last dose of study drug.

After the Safety Follow-Up visit, all medications related to reportable SAEs and ECIs as defined in Section 7.2, should be recorded.

All new anti-cancer therapy initiated after the study start must be recorded in the eCRF. If a subject initiates another anti-cancer therapy other than the assigned study treatment(s), the study treatment(s) should be discontinued and the subject will move into the survival follow-up phase; if a subject initiates a new anti-cancer therapy within 30 days after the last dose of the trial treatment, the 30 day Safety Follow-up visit should occur before the first dose of the new therapy.

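### Section 5.5.2 takes a subject who needs a listed prohibited treatment while on study out of the trial, whereas 5.5, 5.8 and 7.1 stop only study treatment and keep the subject in follow-up

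*Combined protocol and SAP*

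**What the plan says.** Section 5.5.2 lists therapies barred in the Screening and Treatment Phases: systemic anti-cancer therapy, other immunotherapy, other investigational agents, radiation, live vaccines and systemic glucocorticoids, with some exceptions. It then says that subjects who, in the investigator's view, "require the use of any of the aforementioned treatments for clinical management, should be removed from the trial".

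Other current text gives a different consequence:

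- Section 5.5, the parent section, says only that "discontinuation from trial therapy or vaccination may be required".
- Section 5.5.2.1 says that subjects needing the treatments it refers to should be discontinued, without saying from what. For a Table 11 CYP drug that is medically necessary and has no alternative, "then the subject must discontinue treatment with preladenant".
- Section 5.8.1 opens with "Discontinuation of treatment does not represent withdrawal from the trial" and adds that "all subjects who discontinue trial treatment prior to completion of the treatment period will still continue to participate in the trial".
- Section 5.8.2 makes withdrawn consent the ground on which a subject must be withdrawn. After withdrawal, "they will no longer receive treatment or be followed at scheduled protocol visits".
- Section 7.1.1.6.2 says that when another anti-cancer therapy is started, "the study treatment(s) should be discontinued and the subject will move into the survival follow-up phase". Section 7.1.5.3.4 agrees.

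Section 5.2.1.4 closes its list of reasons for ending treatment, which includes progression and unacceptable toxicity, with "administrative reasons requiring cessation of treatment, at which point they will be discontinued from the study". Section 1.0 has the same ending.

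**The concern.** Stopping study treatment and leaving the trial have different consequences for the data. After the first, a subject still contributes adverse events, scans and survival status. After the second, scheduled follow-up ends. Section 5.5.2 names the second where the sections that govern follow-up name the first, so two sites facing the same event could collect different data.

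The loss would not be random. A need for non-protocol anti-cancer therapy or radiation during treatment is tied to progression or illness, so survival times cut off at removal would be censored at a point related to prognosis. Adverse events after Cycle 1 serve the primary safety objective, and section 2.1 says the final RP2D draws on late as well as early toxicities. The Summary of Changes explains that collection runs to 90 days so that late toxicities of immunomodulatory agents are captured.

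**Working it through.** The plan gives no figure to reproduce here. The check sets the rules side by side and asks what each type of subject would lose.

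**Step 1. What each rule ends.**

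| Section | Trigger | What ends | Follow-up afterwards |
|---|---|---|---|
| 5.5.2 | Need for a listed treatment in Screening or Treatment Phase | Place in the trial | None stated |
| 5.5 | Clinical indication for a prohibited medication | Trial therapy, possibly | Not stated |
| 5.5.2.1 | Need for a restricted treatment; a Table 11 CYP drug | Unspecified; preladenant for CYP drugs | Not stated |
| 5.8.1 | Early stop of study treatment | Study treatment | Continues per flow chart |
| 5.8.2 | Withdrawn consent | Place in the trial | No scheduled visits |
| 7.1.1.6.2, 7.1.5.3.4 | Another anti-cancer therapy | Study treatment | Survival phase |

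For one event, starting non-protocol anti-cancer therapy while on treatment, 5.5.2 and 7.1.1.6.2 give opposite instructions on follow-up. Table 11 also lists chemotherapy, biologics, investigational drugs and radiation, so these fall under both 5.5.2 and 5.5.2.1.

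**Step 2. How far 5.5.2 reaches.** It applies only in the Screening and Treatment Phases, and 5.5.2.2 says no therapy is prohibited in post-treatment follow-up. Radiation to a symptomatic solitary lesion or to the brain may be allowed. Steroids have exemptions in 5.5.2 and wider ones in 5.5.2.2. A subject removed during screening has had no study treatment, so the follow-up question concerns treated subjects.

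**Step 3. What a literal reading of 5.5.2 would cost.**

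| Situation | Follow-up in 7.1.2.6 and 7.1.5.3 | Lost if 5.5.2 is read literally |
|---|---|---|
| Non-protocol anti-cancer therapy started while on treatment | Adverse events to 30 days, or to the day of new therapy if that falls between 30 and 90 days; imaging ends at new therapy; survival calls every 12 weeks | Mainly the survival calls |
| Non-exempt radiation, non-exempt systemic steroids, live vaccine | Adverse events to 90 days; imaging every 9 weeks until progression or another stopping event; then survival calls | All three |
| Next-line therapy begun after study treatment has ended | As in the first row | Nothing; 5.5.2 does not apply |

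The follow-up sections do not say whether radiation counts as a new anti-cancer therapy. If a site treats it so, radiation moves to the first row.

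**Step 4. Which analyses are touched.** The primary endpoint is the DLT rate, observed in Cycle 1. Section 5.2.2.1 already makes a subject who must take a prohibited medication in Cycle 1 non-evaluable and replaced, unless the medication treats a drug-related event. That endpoint is therefore little affected. The data at risk are adverse events after Cycle 1, post-treatment scans in subjects without progression, and overall survival, which is exploratory.

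**Step 5. Size.** The documents give no rate for on-study need of a listed treatment. As a scale only, with assumed rates and the planning target of 112 subjects: 0.05 × 112 = 5.6, 0.10 × 112 = 11.2 and 0.20 × 112 = 22.4, or about 6, 11 and 22 subjects. These figures do not net out the exemptions in Step 2 or the follow-up that already ends under Step 3.

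**The case against.** The strongest reply is that 5.5.2 is one loose sentence among sections that otherwise agree. Its parent section speaks of trial therapy, 5.8.1 covers everyone who stops treatment early, and 5.8.2 does not list prohibited treatment as a ground for withdrawal. On that view a sensible site reads the sentence as off treatment. This is a fair reading, but nothing in 5.5.2 tells the site to adopt it, and the words used point the other way. The objection lowers the likely frequency of the problem without removing the contradiction.

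The reply also disposes of several stronger inferences that a reader might draw:

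- **That every subject who progresses to next-line therapy is lost.** The limit to the Screening and Treatment Phases, and the closing sentence of 5.5.2.2, rule this out when study treatment has already stopped.
- **That subjects with immune toxicity are removed because they need steroids.** The exemption within 5.5.2 is narrow, but it refers to 5.5.2.2, which allows steroids for adverse events. Table 8 calls for them without removal from the trial.
- **That each removed subject loses the full safety and imaging schedule.** For those starting anti-cancer therapy, adverse event collection is already shortened and imaging already ends. Section 7.1.4.1 requires end-of-treatment procedures and follow-up of events present even at withdrawal. Section 7.2.3.1 keeps related serious events reportable at any time.
- **That 1.0 and 5.2.1.4 show follow-up ending at progression.** Section 1.0 itself requires 90 days of monitoring after treatment discontinuation and allows cross-over at progression, and 2.1 requires survival calls after confirmed progression. In context the phrase is imprecise wording for stopping treatment.

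**Conclusion.** The point holds in limited form. Section 5.5.2 contradicts 5.5, 5.8.1, 5.8.2, 7.1.1.6.2 and 7.1.5.3.4 on whether a treated subject who needs a listed treatment during the Treatment Phase stays in follow-up. Applied literally, it would cost survival follow-up in one group, and late adverse events, imaging and survival follow-up in a probably smaller group, with clinical need selecting who is lost.

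The conclusion rests on the text alone and on no assumed rate; the counts in the working are only a scale. It does depend on a site reading removal from the trial as the end of follow-up, which the documents neither define nor exclude. The documents do not support a claim that the primary DLT analysis is compromised or that late safety data are lost across the trial. This is a wording defect with a modest, selective effect on data completeness, worth correcting because correction is cheap.

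**What to change.** For treated subjects, reconcile 5.5.2 with 5.8.1. Replace the removal wording with a statement that any resulting stop is a discontinuation of study treatment under 5.8.1, not withdrawal from the trial. Follow-up then continues as already scheduled in 7.1.2.6.3 and 7.1.5.3, including their existing limits once a new anti-cancer therapy starts. A blanket promise to keep all such subjects in safety, imaging and survival follow-up should be avoided: it would contradict 7.1.2.6.2, 7.1.2.6.3, 7.1.5.3.2 and 7.1.5.3.3 for subjects who start anti-cancer therapy.

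In 1.0 and 5.2.1.4, change the closing phrase so that subjects are discontinued from study treatment and not from the study. Reconcile 5.5.2 with 5.5.2.1 on what is stopped when a treatment falls under both; this review does not say which agent should stop or when.

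The cost is amendment wording and a few more follow-up contacts. The visits and calls are already in the flow chart.
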